## VERSION HISTORY

This Statistical Analysis Plan (SAP) for Trial GCT3014-01 is based on the protocol dated 18 February 2022 (Global Amendment 3, version 5.0).

SAP Version	Approval Date	Change	Rationale
1		Not Applicable	Original version

## Abbreviations

AE	adverse event
AUC	area under the curve
AUC0-168h	area under the concentration-time curve from time zero to 168 hours
AUC0-last	area under the concentration-time curve from time zero to last quantifiable sample
BAS	biomarker analysis set
CBR	clinical benefit rate
CI	confidence interval
CD	cluster of differentiation
CRF	case report form(s) (paper or electronic as appropriate for this study)
Cmax	maximum concentration
Ctrough	lowest level before dosing
DBL	database lock
DCO	data cut-off
DDS	dose determining dataset
DLT	dose limiting toxicities
DNA	deoxyribonucleic acid
DOR	duration of response
DPS	data presentation specification
ECG	electrocardiogram
FLC	free light chain
FPD	first subject dosed
FPI	first subject in
H2H	head-to-head
IAS	immunogenicity analysis set
IFE	immunofixation
Ig	immunoglobulin
IMWG	International Myeloma Working Group
KM	Kaplan-Meier
MedDRA	Medical Dictionary for Regulatory Activities
MRD	minimal residual disease
MRD-	minimal residual disease negativity
MTD	maximum tolerated dose
NK	natural killer
ORR	objective response rate
OS	overall survival
PAS	pharmacokinetic analysis set
PFS	progression free survival
PK	pharmacokinetics
R A,AUC	accumulation ratio in AUC
R A,Cmax	accumulation ratio in Cmax
RES	response evaluable set
RNA	ribonucleic acid
R/R AML	relapsed or refractory acute myeloid leukemia
R/R DLBCL	relapsed or refractory diffuse large B-cell lymphoma
RP2D	recommended phase 2 dose
RRMM	relapsed or refractory multiple myeloma
SAE	serious adverse event
Std Dev	standard deviation
Tmax	time to maximum concentration

TLF	tables, listings, and figures
TTR	time to response

### ***Response abbreviations***

#### ***IMWG- RRMM***

MRD-	MRD-negative
sCR	Stringent complete response (included in ORR)
CR	Complete response (included in ORR)
VGPR	Very good partial response (included in ORR)
PR	Partial response (included in ORR)
MR	Minimal response
SD	Stable disease
PD	Progressive disease

#### ***Lugano – R/R DLBCL***

CR	Complete response (included in ORR)
PR	Partial response (included in ORR)
SD	Stable disease
PD	Progressive disease

#### ***IWG -R/R AML***

CR	Complete remission (included in ORR)
CRi	Complete remission with incomplete hematological recovery (included in ORR)
CRp	Complete remission with incomplete platelet recovery (included in ORR)
PR	Partial remission (included in ORR)
MLFS	Morphologic leukemia-free state (included in ORR)
SD	Stable disease
DP	Disease progression
R	Relapse

## 1 INTRODUCTION

This statistical analysis plan describes in detail the analysis of the endpoints for trial GCT3014-01. GEN3014 (HexaBody®-CD38) is a fully human immunoglobulin (Ig)G1 monoclonal antibody (mAb) targeting the cluster of differentiation (CD)38 antigen. As compared to daratumumab, GEN3014 has a higher affinity for CD38, more potent CDC activity, and stronger inhibition of the CD38 cyclase activity. It is hypothesized that GEN3014 may trigger stronger reversion of the immune suppression in the tumor microenvironment.

GCT3014-01 comprises the following parts (see [Figure 1](#)):

- Phase 1 Dose Escalation Part
  - Dose escalation in RRMM
  - Dose escalation in R/R AML
- Phase 2 Expansion Part A
  - Expansion arm in anti-CD38 mAb-naïve RRMM
  - Expansion arm in anti-CD38 mAb-refractory RRMM
  - Expansion arm in R/R DLBCL
  - Expansion arm in R/R AML
- Phase 2 Expansion Part B
  - A randomized H2H comparison of GEN3014 IV versus daratumumab SC in anti-CD38 mAb-naïve RRMM

The main analysis reporting difference between the parts is the ordering of objectives and the grouping of summary statistics. In the Dose Escalation, the primary objective is to determine the safety profile (summarized by DLTs, AEs and safety laboratory parameters), while in Phase 2 Expansion it is to further characterize the antitumor activity based on disease specific response evaluations:

- The International Myeloma Working Group consensus criteria (IWMG) 2016 for RRMM,
- The revised response criteria 2014 for Hodgkin and non-Hodgkin lymphoma (Lugano classification) for R/R DLBCL, and
- The International Working Group (IWG) 2003 response criteria for R/R AML.

The grouping factor in Dose Escalation is the dose level per disease type while in Phase 2 Expansion the results will be summarized by the (disease) cohort. Besides this and the different disease specific response criteria, the underlying details of the analyses and the statistical methodologies do not differ between escalation and expansion, or between diseases. This SAP is thus used for both parts, with above differences noted. To ease the presentation of the planned analysis, the word “cohort” will be used throughout, but this can also be thought of as the dose level in Dose Escalation. Layouts, programming notes and titles for the tables, listings and figures are further specified in the Data Presentation Specification (DPS).

## 1.1 Objectives and Endpoints

**Table 1: Phase 1 Dose Escalation**

Objectives	Endpoints
Primary	

 
Determine the RP2D and if reached, the MTD of GEN3014
 
	
 
Incidence of DLTs
 

 
Evaluate the safety and tolerability of GEN3014
 
	
 
Safety: Incidence and severity of AEs and SAEs, including changes in laboratory values, vital signs, ECGs
 
Tolerability: Dose interruptions, delay, and dose intensity
 

Secondary	

 
Characterize the PK properties of GEN3014
 
	
 
Noncompartmental PK parameters (if feasible): 
 
Cmax
 
tmax
 
Ctrough
 
AUC0-last and AUC0-168h
 
RA,Cmax and RA,AUC
 
 
 
In addition, a population PK modeling approach may be employed
 

 
Characterize the pharmacodynamic properties of GEN3014
 
	
 
Pharmacodynamic markers in blood and tumor samples, including frequencies of NK cells and other leukocyte subsets and complement analyses
 

 
Evaluate immunogenicity
 
	
 
Anti-GEN3014 antibodies
 

 
Assess the preliminary anti-tumor activity of GEN3014
 
	
 
ORR
 
CBR
 
DOR
 
TTR
 

 
Assess the clinical efficacy of GEN3014
 
	
 
Progression-free survival (PFS)
 
Overall survival (OS)
 

Exploratory	

 
Assess potential biomarkers predictive of clinical response to GEN3014
 
	
 
Expression of CD38 and other molecular markers on tumor cells at baseline and during treatment
 

 
Assess minimal residual disease (MRD) status
 
	
 
Rate of MRD-negative remission in RRMM
 


 
Explore PK/pharmacodynamic relationship (PK/antitumor activity) and PK/safety
 
	
 
Dose concentration response (biomarkers and/or efficacy, safety) relationship
 

AE=adverse event; AUC0-last=area under the concentration-time curve from time zero to last quantifiable sample; AUC0-168h=area under the concentration-time curve from time zero to 168 hours; CBR=clinical benefit rate; CD=cluster of differentiation; Cmax=maximum concentration; Ctrough=predose concentration; DLT=dose-limiting toxicity; DOR=duration of response; ECG=electrocardiogram; MTD=maximum tolerated dose; NK=natural killer; ORR=objective response rate; PK=pharmacokinetic(s); RA,AUC=accumulation ratio in AUC; RA,Cmax=accumulation ratio in Cmax; RP2D=recommended phase 2 dose; RRMM=relapsed or refractory multiple myeloma; SAE=serious adverse event; tmax=time to maximum concentration; TTR=time-to-response.

**Table 2: Phase 2 Expansion Part A**

Objectives	Endpoints
Primary	

 
Assess the preliminary anti-tumor activity of GEN3014
 
	
 
ORR
 

Secondary	

 
Evaluate anti-tumor activity and efficacy of GEN3014
 
	
 
CBR
 
DOR
 
TTR
 
PFS
 
OS
 

 
Evaluate safety of GEN3014
 
	
 
Safety: Incidence and severity of AEs and SAEs, including changes in laboratory values, vital signs, ECGs
 
Immunogenicity: Anti-GEN3014 antibodies
 

 
Characterize the PK of GEN3014
 
	
 
Noncompartmental PK parameters (if feasible): 
 
<math>C_{max}</math>
 
<math>t_{max}</math>
 
<math>C_{trough}</math>
 
<math>AUC_{0-last}</math> and <math>AUC_{0-168h}</math>
 
<math>RA_{Cmax}</math>, <math>RA_{AUC}</math>, and <math>RA_{Ctrough}</math>
 
 
 
In addition, a population PK modeling approach may be employed
 

 
Evaluate the pharmacodynamic profiles of GEN3014
 
	
 
Pharmacodynamic markers in blood and tumor samples, including frequencies of NK cells and other leukocyte subsets, and complement analyses
 

Exploratory	

 
Assess potential biomarkers predictive of clinical response to GEN3014 and evaluate potential surrogacy with PFS and OS
 
	
 
CCI
 
Immune cell profiling
 
DNA mutation status and gene profile (RNA-seq)
 

 
Assess MRD status
 
	
 
Rate and duration of MRD-negative remission in RRMM, R/R AML, R/R DLBCL
 

 
Explore PK/pharmacodynamic relationship (PK/anti-tumor activity) and PK/safety
 
	
 
Dose concentration response (biomarkers and/or efficacy, safety) relationship
 

[figure not shown]
AE=adverse event;  $AUC_{0-last}$ =area under the concentration-time curve from time zero to last quantifiable sample;  $AUC_{0-168h}$ =area under the concentration-time curve from time zero to 168 hours; CBR=clinical benefit rate; CD=cluster of differentiation;  $C_{max}$ =maximum concentration;  $C_{trough}$ =predose concentration; DNA=deoxyribonucleic acid; DOR=duration of response; ECG=electrocardiogram; MRD=minimal residual disease; MTD=maximum tolerated dose; NK=natural killer; ORR=objective response rate; OS=overall survival; PFS=progression-free survival; PK=pharmacokinetic(s);  $RA_{AUC}$ =accumulation ratio in AUC;  $RA_{Cmax}$ =accumulation ratio in  $C_{max}$ ;  $RA_{Ctrough}$ =accumulation ratio in  $C_{trough}$ ; RNA=ribonucleic acid; RP2D=recommended phase 2 dose; R/R AML=relapsed or refractory acute myeloid leukemia; R/R DLBCL=relapsed or refractory diffuse large B-cell lymphoma; RRMM=relapsed or refractory multiple myeloma; OS=overall survival; SAE=serious adverse event; seq=sequencing;  $t_{max}$ =time to maximum concentration; TTR=time-to-response.

**Table 3: Phase 2 Expansion Part B**

Objectives	Endpoints
Primary	

 
Compare overall response of GEN3014 IV vs daratumumab SC in anti-CD38 mAb-naïve RRMM subjects
 
	
 
ORR
 

Secondary	

 
Compare time dependency in PK between GEN3014 IV vs daratumumab SC
 
	
 
Ctrough levels of GEN3014 IV, or daratumumab SC, on Cycle 3 Day 1
 

 
Assess the anti-tumor activity of GEN3014 IV vs daratumumab SC
 
	
 
VGPR or better
 
CR or better
 
DOR
 
TTR
 
PFS
 
OS
 
Time to next therapy (TTNT)
 

 
Assess safety of GEN3014 IV vs daratumumab SC
 
	
 
Safety: Incidence and severity of AEs and SAEs, including changes in laboratory values, vital signs, ECGs
 
Immunogenicity: Anti-GEN3014 antibodies, anti-daratumumab antibodies, anti- rHuPH20 antibody
 

Exploratory	

 
Evaluate the pharmacodynamic profiles of GEN3014 and compare with those of daratumumab
 
	
 
Pharmacodynamic markers in blood and tumor samples, including frequencies of NK cells and other leukocyte subsets, and complement analyses
 

 
Assess potential biomarkers predictive of clinical response to GEN3014 and evaluate potential surrogacy with PFS and OS
 
	
 
CCI
 
Immune cell profiling
 
DNA mutation status and gene profile (RNA-seq)
 

 
Assess MRD status
 
	
 
Rate and duration of MRD-negative remission
 

 
Explore PK/pharmacodynamic relationship (PK/anti-tumor activity) and PK/safety
 
	
 
Dose concentration response (biomarkers and/or efficacy, safety) relationship
 

AE=adverse event; CR=complete remission; Ctrough=predose concentration; DNA=deoxyribonucleic acid; DOR=duration of response; ECG=electrocardiogram; H2H=head-to-head; IV=intravenous(ly); mAb=monoclonal antibody; MRD=minimal residual disease; NK=natural killer; ORR=objective response rate; OS=overall survival; PK=pharmacokinetic(s); PFS=progression-free survival; RNA=ribonucleic acid; RRMM=relapsed or refractory multiple myeloma; SAE=serious adverse event; SC=subcutaneous; seq=sequencing; TTR=time-to-response; VGPR=very good partial response.

## 1.2 Trial Design

**Figure 1: Trial Design**

### Key trial characteristics

- Dose Escalation is guided by modified BOIN rules
- Interim analyses are planned as follows in Expansion Part A:
  - Anti-CD38 mAb-naïve RRMM: When the initial 10 response evaluable subjects (including subjects who received GEN3014 at 16 mg/kg or 24 mg/kg from Dose Escalation Part A) have completed  $\geq 2$  cycles of GEN3014 treatment
  - R/R DLBCL: When the initial 20 response evaluable subjects have completed  $\geq 2$  cycles of GEN3014 treatment
- Data from the Dose Escalation and the Expansion cohorts may be analyzed separately.
- Primary safety and efficacy analyses based on the Dose Escalation data will be conducted on all subject data at the end of the Dose Escalation, in conjunction with declaring RP2D, at latest 6 months after last subject first dose. Separate deliveries may be planned for the RRMM and R/R AML disease cohorts as feasible.
  - Note: The delivery containing the primary safety and efficacy analysis in RRMM will be taken as the delivery supporting the clinical overview addendum that includes dose escalation data in RRMM.
- The primary analysis of each expansion cohort in Parts A and B will be conducted on all subject data, at latest 6 months after last subject first dose in respective expansion cohort.
- The final analyses will be reported as an addendum to the primary analyses, based on the accumulated data up to 5 years after study start.

Further trial design details are provided in the protocol.

### Subject-wise considerations

- First dose of GEN3014 is administered in split dose to mitigate risk of infusion related reactions.
- For each subject, the trial is partitioned into a screening phase, a treatment phase, a safety follow-up phase, and a survival follow-up phase. Not all phases need to be initiated.

### 1.3 Randomization and Blinding

The 1:1 randomization between GEN3014 and daratumumab SC in Expansion Part B will be stratified by body weight at baseline ( $\leq 70$  kg vs  $> 70$  kg), CCI [REDACTED]. The randomization will be administered through a centralized IRT system which will dictate the treatment assignment and matching study drug kit for the subject. The randomization is not blinded.

## 2 STATISTICAL HYPOTHESES

There are no pre-defined hypotheses for GCT3014-01. The Dose Escalation part is designed to determine the RP2D and MTD (if reached), and the Expansion Part A explores the anti-tumor activity of GEN3014.

In the Expansion Part B (Randomized H2H), the response ratio and the geometric mean ratio of  $C_{trough}$  on Cycle 3 Day 1 will be derived to describe the proportion of effect of daratumumab SC retained by GEN3014 IV as compared to daratumumab SC. The comparison serves as a preliminary estimation of the relative effect of the two anti-CD38 mAb molecules.

## 3 SAMPLE SIZE

### Dose Escalation

- Up to 54 subjects with RRMM will be treated including subjects who are anti-CD38 mAb-naïve.
- Up to 18 subjects with R/R AML will be treated.

### Expansion Part A

- Anti-CD38 mAb-naïve RRMM (N=approximately 10 subjects)
- Anti CD38 mAb-refractory RRMM (N=20 subjects)
- R/R DLBCL (up to 40 subjects)
- R/R AML (N=20 subjects)

Expansion Part B will include approximately 80 anti-CD38 mAb-naïve RRMM subjects randomized to GEN3014 or daratumumab SC in a 1:1 ratio (N=40 each cohort).

## 4 ANALYSIS SETS

### 4.1 Full Analysis Set (FAS)

The FAS and safety set are defined in the same way and will comprise all enrolled subjects who receive at least 1 dose of trial drug (GEN3014 or daratumumab SC). The treatment effect will be assessed by the actual treatment given, i.e. subjects will be categorized by their actual treatment.

The FAS will be used to summarize efficacy and safety analyses.

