#### 4.1.4 Expansion Part B (Randomized H2H)

If the preliminary efficacy and safety are judged to be favorable in the initial 10 anti-CD38 mAb-naïve subjects with RRMM who received 16 mg/kg or 24 mg/kg (in the Dose Escalation or Expansion Part A), approximately 80 anti-CD38 mAb-naïve subjects with RRMM will be randomized in a 1:1 ratio to receive:

- GEN3014 IV at the RP2D (N=40), or
- Daratumumab SC at the approved dose of 1800 mg (N=40)

The aim of the head-to-head comparison between GEN3014 IV and daratumumab SC is to evaluate the efficacy and maximum Cycle 3 Day 1 Ctrough level of study treatments in at least 40 subjects on each treatment arm. To ensure the collection of sufficient efficacy, PK, and safety data, after approximately 80 subjects are randomized, additional enrollment to either treatment arm can be implemented to replace:

- Subjects who are randomized but never receive the study treatment; and/or
- Subjects who discontinue the study treatment prematurely prior to the Cycle 3 Day 1 dosing

A maximum of 90 subjects will be treated.

The administration schedule will be the same as in the Dose Escalation (see Section 6.1), except that the first dose of daratumumab SC will not be split between Days 1 and 2.

Randomization will be stratified by body weight at baseline ( $\leq 70$  kg vs  $> 70$  kg), CCI [REDACTED]. See Sections 5.1.3 and 5.2.2 for inclusion and exclusion criteria.

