#### **6.4.2.2 Expansion Part A (GEN3014 Single Cohorts) and Part B (Randomized H2H)**

In the Expansion Part A (GEN3014 Single Cohorts), subjects will be assigned to 1 of the 4 cohorts: anti-CD38 mAb-naive RRMM, anti-CD38 mAb-refractory RRMM, R/R AML, or R/R DLBCL.

In the Expansion Part B (Randomized H2H), anti-CD38 mAb-naive subjects with RRMM will be randomized in a 1:1 ratio to receive either GEN3014 or daratumumab SC. Subjects will be assigned randomly to 1 of the 2 treatment groups based on a computer-generated randomization schedule prepared before the trial by or under the supervision of the sponsor. The randomization will be balanced by using randomly permuted blocks and will be stratified by body weight at baseline ( $\leq 70$  kg;  $> 70$  kg) CCI [REDACTED]. The IRT will assign a unique treatment code, which will dictate the treatment assignment and matching study drug kit for the subject. The requestor must use their own user identification and personal identification number when contacting the IRT and will then give the relevant subject details to uniquely identify the subject. In order to ensure 40 evaluable subjects in each treatment arm (see Section 4.1.4 and Section 9.2.3), the sponsor may replace subjects by arm rather than stratification factors, if justified.

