## 9 STATISTICAL CONSIDERATIONS

The statistical analysis of the data collected in this trial is the responsibility of the sponsor. The objectives and endpoints for the 3 trial parts are tabulated in [Table 3-1](#) (Dose Escalation), [Table 3-2](#) (Expansion Part A [GEN3014 Single Cohorts]), and [Table 3-3](#) (Expansion Part B [Randomized H2H]). This section will (without particular reference to trial part) outline the planned analysis for each endpoint. The analyses will be detailed further in the Statistical Analysis Plan (SAP) to be finalized before database lock.

All presentations will be done separately for the different trial parts. Subjects in the Dose Escalation part will be analyzed according to the DL received. Subjects in Expansion Part A (GEN3014 Single Cohorts) will be analyzed according to their assigned expansion cohort. Subjects in Expansion Part B (Randomized H2H) will be analyzed according to their assigned treatment.

Statistical deliveries (tables, listings, and figures) may be produced for the following milestones:

- Periodic DMC reviews
- **Dose Escalation:** Primary safety and efficacy analyses will be conducted on all subject data at the end of the escalation, at latest 6 months after last patient first dose. Separate deliveries may be planned for the RRMM and R/R AML disease cohorts as feasible.
- **Expansion Part A (GEN3014 Single Cohorts)** consists of 4 parallel cohorts:
  - Anti-CD38 mAb-naive RRMM cohort
  - Anti-CD38 mAb-refractory RRMM cohort
  - R/R DLBCL cohort
  - R/R AML cohort

Each cohort will assess the disease-specific anti-tumor activity of GEN3014. No comparisons between cohorts are planned. Each cohort may report its individual primary analysis. The primary analyses will be conducted on all subject data, at latest 6 months after last patient first dose in respective expansion cohort. Timing of futility analyses in DLBCL cohort is described below.

- **Expansion Part B (Randomized H2H)** in anti-CD38 mAb-naive RRMM subjects: Primary safety and efficacy analyses will be conducted on all subject data, at latest 6 months after last patient first dose.
- The final analyses will be reported as an addendum to the primary analyses, based on the accumulated data up to 5 years after study start.

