## **9.2.3 Expansion Part B (Randomized H2H): Comparison of GEN3014 IV vs Daratumumab SC in Anti-CD38 mAb-naïve RRMM Subjects**

The comparison of the 2 anti-CD38 mAb molecules will be based on approximately 40 evaluable subjects treated with GEN3014 IV vs 40 evaluable subjects treated with daratumumab SC. The ratio in the response rates between the 2 arms will be described using the Miettinen-Nurminen method ([Newcombe, 1998](#)).

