## **9.3 Populations for Analyses**

**Full Analysis Set (FAS):** The FAS and safety set are defined in the same way and will comprise all enrolled subjects who receive at least 1 dose of trial drug (GEN3014 or daratumumab SC). In case of any deviations from planned dosing, subjects will be treated as per actual dosing.

The FAS will be used to summarize efficacy and safety analyses.

**Response Evaluable Set (RES):** Comprises all subjects in the FAS that at the timing of data cutoff date (for any interim reporting of the ongoing data):

- have measurable disease at baseline;
- had  $\geq 1$  on-treatment disease assessment;
- have died within 60 days of first trial treatment without post-baseline disease assessment (these are included as non-responders)

**Safety Set:** See definition for FAS.

**Per-Protocol Set:** Not applicable

**Dose-Determining Analysis Set (DDS):** The DDS will include all FAS subjects in the Dose Escalation part who meet the minimum exposure criterion and have sufficient safety evaluations or experience a DLT during the first 28 days of dosing (ie, in Cycle 1).

A subject will meet the minimum exposure criterion if the subject receives 4 out of the 4 preplanned doses during the DLT period. (The 2 initial split doses in Day 1 and Day 2 account for 1 preplanned dose.)

**Pharmacokinetic Analysis Set 1 (PAS1):** The PAS1 will include all enrolled subjects who receive at least 1 dose of trial drug (GEN3014 or daratumumab SC) and who provide at least 1 evaluable PK sample.

**Pharmacokinetic Analysis Set 2 (PAS2):** The PAS2 will include all enrolled subjects who received all 8 weekly GEN3014 or daratumumab SC doses in Cycles 1 and 2 with the cumulative dose administered amounting to 80% to 125% of the planned dose and provided a predose PK blood sample on Cycle 3 Day 1.

**Immunogenicity Analysis Set (IAS):** The IAS will include all enrolled subjects who receive at least 1 dose of trial drug (GEN3014 or daratumumab SC) and have a baseline and at least 1 evaluable on-treatment ADA sample.

**Biomarker Analysis Set (BAS):** The BAS will include all enrolled subjects who receive at least 1 dose of trial drug (GEN3014 or daratumumab SC) and have at least 1 evaluable biomarker sample.

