#### ***5.3.1 Definition of Endpoint(s)***

ORR is defined as the proportion of subjects in the analysis population (FAS is used for primary analysis) with a BOR of partial response (PR) or better according to the disease specific criteria. In detail, the disease-specific definitions of ORR are

- RRMM: a BOR of PR, VGPR, CR or sCR
- R/R DLBCL: a BOR of PR or CR
- R/R AML: a BOR of MLFS, PR, CRp, CRi, or CR.

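### Part B's primary response ratio should follow the randomisation: the documents disagree on assigned versus actual treatment, and subjects randomised but never dosed drop out of the analysis

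*SAP*

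**What the plan says.** **Arm used for analysis.** Protocol Section 9: "Subjects in Expansion Part B (Randomized H2H) will be analyzed according to their assigned treatment". SAP 4.1: "The treatment effect will be assessed by the actual treatment given, i.e. subjects will be categorized by their actual treatment". Protocol 9.3 sides with the SAP: where dosing departs from plan, subjects are handled by what they received. The protocol therefore also disagrees with itself.

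**Who is analysed.** Under Protocol 9.3 the FAS "will comprise all enrolled subjects who receive at least 1 dose of trial drug", and SAP 4.1 has the same rule. SAP 5.3.1, defining ORR, adds "FAS is used for primary analysis". SAP 5.3.3 plans no sensitivity analyses. Neither document defines an all-randomised set.

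**Replacement.** Protocol 4.1.4 allows additional enrolment to either arm to replace two groups. The first is "Subjects who are randomized but never receive the study treatment; and/or"; the second is subjects who stop before Cycle 3 Day 1 dosing. At most 90 subjects are to be treated. Under Protocol 6.4.2.2, to secure 40 evaluable subjects per arm, "the sponsor may replace subjects by arm rather than stratification factors, if justified". Protocol 9.2.3 says the comparison "will be based on approximately 40 evaluable subjects treated with GEN3014 IV vs 40 evaluable subjects treated with daratumumab SC". Part B is open-label.

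**Status of the comparison.** Protocol 9.1 states no hypotheses and calls the comparison a preliminary estimate. Protocol 9.4.3.1 reports the response ratio with a Miettinen-Nurminen 95% interval and no P values.

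**The concern.** Part B is the trial's only randomised comparison, and comparing response is its primary objective. The two arms are exchangeable only as randomised. A set defined by later dosing, with arms defined by the drug received, gives up that protection. Anyone deciding after randomisation whether a subject starts treatment can know the arm, because the trial is open-label. If loss before dosing differs between a new IV agent and an approved SC drug, the ratio is biased, in a direction that cannot be known in advance.

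PFS, OS and time to next therapy have a related mismatch. Their clock starts at randomisation, but membership of the set depends on a later event.

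There is also a practical problem. A programmer cannot follow both Protocol Section 9 and SAP 4.1. The SAP's version history says it is based on Amendment 3; the current protocol is Amendment 5, and the SAP does not mention replacement. Its appendix on changes to protocol-planned analyses reads as not applicable.

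**Working it through.** **1. What happens to each kind of randomised subject**

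| Randomised subject | In the FAS? | Counted in ORR as |
|---|---|---|
| Never dosed | No | Left out; may be replaced |
| Dosed, stops before Cycle 3 Day 1 | Yes | Observed best response; may also be replaced |
| Dosed, never assessed | Yes | Non-responder (ORR is a proportion of the whole FAS) |
| Dosed with the other arm's drug | Yes | Under the drug received (SAP 4.1), or the assigned drug (Protocol Section 9) |

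Only the first and last rows depart from an as-randomised analysis.

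**2. Inputs**

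- 40 per arm, from Protocol 4.1.4 and 9.2.3: 2 × 40 = 80. The cap of 90 treated leaves 90 − 80 = 10 beyond plan.
- No alpha, power or precision target is given for Part B, so there is no sample-size figure to reproduce.
- Response rate 40%. Protocol 9.5.1 uses it for the lead-in analysis, where P(at least 2 of 10 respond) = 0.954 reproduces the stated 95%. Applying it to both Part B arms is an assumption: 0.40 × 40 = 16 responders each.
- The number k of undosed subjects is not in the documents; k = 2, 4 and 5 in one arm are shown.

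**3. Ratio in the FAS**

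GEN3014 over daratumumab = (16/40)/(16/40) = 1.00. The Miettinen-Nurminen limits are the values R solving

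(p1 − R·p2)² / {[q1(1 − q1)/n1 + R²·q2(1 − q2)/n2] × N/(N − 1)} = 1.96²

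where p1 and p2 are the observed rates, q1 and q2 the maximum-likelihood rates constrained to q1 = R·q2, and N = n1 + n2. Result: 0.58 to 1.72.

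**4. Ratio as randomised**

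Suppose k undosed subjects in one arm were replaced, so that 40 were dosed. Restoring them as non-responders makes that arm 16/(40 + k).

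- Undosed on daratumumab: ratio = (16/40)/(16/(40 + k)) = (40 + k)/40.
- Undosed on GEN3014: ratio = 40/(40 + k).

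| k | Undosed on daratumumab | Undosed on GEN3014 |
|---|---|---|
| 2 | 42/40 = 1.05 (0.61 to 1.81) | 40/42 = 0.95 (0.55 to 1.64) |
| 4 | 44/40 = 1.10 (0.64 to 1.90) | 40/44 = 0.91 (0.53 to 1.57) |
| 5 | 45/40 = 1.125 (0.65 to 1.95) | 40/45 = 0.89 (0.51 to 1.54) |

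**5. Assigned versus actual arm**

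If one responder randomised to daratumumab received GEN3014, grouping by actual treatment gives (17/41)/(15/39) = 1.08 instead of 1.00. Two such responders give (18/42)/(14/38) = 1.16.

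**The case against.** **Part B is descriptive.** This stands. No type I error or power is at stake, and shifts of 5% to 12.5% are small beside an interval of 0.58 to 1.72. But that interval reflects sampling variation only; it does not cover selection after randomisation.

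**Assigned and actual arms will rarely differ.** This largely stands. The IRT dictates the assignment and the kit, and site staff give either an infusion or an injection, so a switch would need a gross error. A reader might infer that Part B becomes an as-treated comparison. In practice the SAP wording changes the result only if such an error occurs.

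**Undosed subjects will be visible.** SAP 5.2 plans CONSORT flow diagrams and counts of each analysis set. That lets a reader see the loss, but no analysis is planned that accounts for it.

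**Replacement by arm serves a stated aim.** Protocol 4.1.4 wants efficacy and Cycle 3 Day 1 trough data in at least 40 subjects per arm. If one arm needed 8 replacements, 10 extra subjects at 1:1 would supply about 10/2 = 5. So there is a real cost to banning it outright.

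**Stronger readings that the documents do not support.**

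- A reader might infer that early failures are replaced and removed, so that 16/45 would be reported as 16/40. Dosed subjects who stop before Cycle 3 Day 1 stay in the FAS, so the stated primary analysis already gives 16/45. The risk lies only in the word *evaluable* in Protocol 9.2.3, which is undefined for ORR.
- A reader might infer that sites will know the arm of the next subject. Protocol 6.4.2.2 permits by-arm replacement where justified, but does not say that sites are told.
- Nothing in the documents shows why subjects would stop early, or that pre-dose loss will differ by arm.

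**Conclusion.** The point holds in this form. The documents contradict each other on the arm used to analyse Part B's primary endpoint. The FAS excludes randomised subjects who are never dosed, a loss the protocol expects, and no planned analysis restores them. Replacement by arm, if used, adds subjects not allocated by the 1:1 randomisation.

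The consequence is avoidable bias in the estimated ratio, of unknown direction. It is about 5% to 12.5% upward or 5% to 11% downward for 2 to 5 undosed subjects in one arm, given 16/40 responders per dosed arm. Both that response rate and those counts are assumptions. If nobody is left undosed, nobody receives the wrong drug and no replacement is placed by arm, the effect is nil.

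**What to change.** 1. Define an all-randomised set for Part B, analysed by assigned arm. Make it primary for ORR, VGPR or better, and CR or better, with undosed subjects as non-responders.
2. Use the same set for PFS, OS and time to next therapy. Censor undosed subjects without follow-up at randomisation. SAP Table 8 needs this added, because its fallback censoring date is Cycle 1 Day 1, which these subjects lack.
3. Keep the dosed, as-treated set for safety and as a supplementary efficacy analysis, and PAS2 for the trough concentration.
4. Reconcile Protocol Section 9, 9.2.3 and 9.3 with SAP 4.1. State that *evaluable* is not the ORR denominator and that replaced subjects stay in the analysis.
5. Place additional subjects through the stratified 1:1 IRT where possible. If by-arm replacement is kept to reach 40 per arm for the trough endpoint, base the primary ORR ratio on subjects allocated by 1:1 randomisation and report it with arm-directed replacements as supplementary.
6. Base the SAP on the current protocol amendment.

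**Cost.** Protocol and SAP wording, and one more analysis set to program. The reported ORR may be slightly lower. Survival follow-up in Protocol 7.1.2 runs from the last dose, so undosed subjects may contribute little to PFS and OS unless some follow-up is arranged. With 1:1 placement, an extra subject may fall in the arm that did not need one, and the trough analysis may fall short of 40 in one arm within the cap of 90.
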